Based on current trends we conservatively estimate that there will be at least 279 kidney transplants from unspecified altruistic donors during that period. Indeed, there were 107 UKD in the UK in 2013. Assuming that the proportion of individuals contacting transplant centres who go on to donate remains stable (36%, based on data from Portsmouth in 2012), we expect that 780 people considering unspecified altruistic donation will contact transplant centres during that period. Based on our previous retrospective study, we expect at least a 80% recruitment rate- that is, 624 in total, of which 224 will go on to donate). This recruitment rate is higher than is typical for longitudinal studies but justifiable given the population being studied. A sample size of 624 will provide sufficient precision to estimate the 95% confidence interval for proceeding to donation to within $\pm 4\%$ overall, and to within $\pm 18\%$ for each centre. In summary, we aim to recruit 224 who have undergone unspecified donation and 400 who failed to donate.

The control group will recruit 200 people who are donating to friend or relative (specified donors) and 200 individuals that intend to donate to a friend or relative but do not (specified non-donors). Based on our retrospective study we expect a recruitment rate of 80%. Therefore, we will need to approach 500 specified donors. Given a stable rate of approximately 1000 specified donations per year across the UK, we anticipate that we will be able to recruit the control group using the same three-year recruitment window as the main cohort. If there is no difference between the unspecified altruistic and specified donors on the physical and psychological variables at 12 months, it will be possible to determine that the lower limit of a one-sided 95% confidence interval will be above the non-inferiority limit of a standardised mean difference of 0.3, which is deemed to be the smallest acceptable clinically meaningful difference – this allows for 20% missing data due to drop-out, at a significance level of 5% with 90% power (14). These individuals will be recruited through transplant co-ordinators nationally.

Amended Recruitment Plan

An amendment was added to the protocol in December 2017, at the request of the Study Steering Committee and with the permission of the funder (NIHR). This was based on recruitment data to June 2017, and driven by a delayed study start and lower than expected recruitment rate.

Amendment

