Extending the period of recruitment for the for the directed donor comparison cohort to December 2018 leads to a revised target sample size of 189. This is close to the original target. Extending the period of recruitment naturally has an impact on the time available for analysis prior to the end of the study in April 2020.

Precision and power with respect to donation rates

The original power calculation indicated that the study, with 624 potential donors, would have sufficient precision to estimate the 95% confidence interval for proceeding to donation to within $\pm 4\%$ overall assuming the donation rate is 35%. Based on the expected 241 prospective unspecified donors to February 2018, precision for the overall donation rate will be approximately $\pm 6\%$, which is still acceptable. Based on the revised estimate of 380, overall precision for the overall donation rate will be approximately $\pm 5\%$.

Precision per centre will be affected to a greater degree. Originally 95% confidence intervals for the donation rate would have been estimated to within $\pm 18\%$ for each centre assuming a donation rate of 36% for each centre. Based on the expected figure by February 2018 and the revised target to December 2018, precision will be approximately $\pm 26\%$ and $\pm 22\%$ for each centre, respectively. This figure is based on a binomial exact confidence interval for the proportion. In the analysis we will use an empirical Bayes estimate, which will provide additional precision since centre level estimates draw on information across centres. A simulation study indicates that using this approach the average precision per centre will be approximately $\pm 13\%$ and $\pm 9\%$ at the centre level, respectively for the expected sample size to February and the revised target to December 2018, respectively. The revised target sample size provides acceptable precision to estimate donation rates. While it will not be possible (or indeed reasonable) to rank centres in terms of donation rates, it will be possible to identify case-mix adjusted rates highlighting centres that are particularly under or over-performing with respect to the average donation rate.

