Outcomes over time for undirected donors will be compared to directed donors. The hypothesis is that undirected donors do no worse than directed donors 12 months after follow-up in terms of mental and physical health. The original target sample size of 224 undirected donors and 200 directed donors provided 80% power to determine non-inferiority of outcomes with a non-inferiority limit equal to a standardised mean difference of no more than .27, which was rounded to .3 in the application and protocol. This allowed for 20% missing data at the 12-month follow up. Given the expected sample size of 87 undirected and 119 directed donors based on recruitment to February 2018, power for a non-inferiority test with the same limit is reduced to 68% assuming 20% missing data. The expected sample size has 80% power when the non-inferiority limit is set at a standardised mean difference of .38. The revised target of 137 prospective unspecified donors and 187 specified donors leads to has 80% power when the non-inferiority limit is set at a standardised mean difference of .32. The non-inferiority limit for the revised target sample size is more acceptable given that it is closer to the minimum important difference for the outcomes considered range between a standardised mean difference of between .3 to .4.

[figure not shown]

Figure 2. Power by non-inferiority limit (standardised mean difference) for original target sample size and expected sample size, accounting for 20% missing data at 12 months.

The revised power calculation with respect to outcomes for undirected compared to directed donors indicated revised target sample size would have 80% power to detect non-inferiority where the bound was a standardised mean difference of $d=.38$, as opposed the original bound of $d=.3$. For the SF12 physical component score (PCS) in undirected donors this relates to a difference of 3.3 units as opposed to 2.6 units; based on the standard deviation of the PCS for unspecified donors in the UK being 8.72 (Maple, H., et al., 2014. *Transplantation*, 98(11), pp.1182-1189.)

Amendment outcomes:

[figure not shown]
In summary, three main changes resulted from the amendment:

1. A reduction in the total recruitment and donation targets across all study populations
2. An extension to the recruitment period (to October 2019)
3. A change in primary focus from the 12-month to the 3-month outcomes data

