To address the issue of potential prolonged work-up time period for UKDs, donors will be asked to provide an estimate of the date of first contact with the transplant services. This will take place at the pre-transplant (Q2) time point. A second supplementary question will be asked at the first post-donation questionnaire (Q3, 3-months) asking donors to describe potential reasons for delays in their work-up process.

Due to a national decline in unspecified donor numbers and changes to the national allocation policy for unspecified donor kidneys, recruitment figures in April 2019 were below those forecasted. Permission was sought, and granted, by the study funder to extend the study recruitment period for a further 3 months (until 31st January 2020).

Consequently, the study's recruitment targets were changed as follows:

Interviews

Qualitative interviews will also be completed with a sample of 15 donors who completed their donation, 15 who withdrew and 15 who are withdrawn by the transplant team from the process. These individuals will be identified from the initial cohort of patients that approached transplant centres with the intention to donate altruistically.

Recruitment Targets

The following recruitment targets have been set:

Focus Groups: 2 focus groups of 8-12 previous donors and 8-12 non-donors.
Total: 16-24 participants

Interviews:

15 potential donors that donated
15 potential donors that did not donate (self-withdrawn)
15 potential donors that did not donate (withdrawn by clinical team)
Total: 45 participants

The following revised minimum recruitment targets have been set:

Questionnaires:

380 potential donors (test population)

- 137 who have donated
- 243 who did not donate

189 specified donors (control population 1) and 189 specified non-donors (control population 2)

Total: 758 participants

Inclusion criteria

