4.2 Follow up Procedures

Follow-up assessments will be sent by post (and made available to complete online). To minimise loss to follow up anyone who has failed to return their 12 months follow up assessments within 14 days will be contacted by phone with the aim of collecting information on at least the primary outcome variable.

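### The primary focus was moved to 3 months, but the hypothesis, power basis and telephone chase stay at 12 months and the endpoints name no primary time

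*Protocol*

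**What the plan says.** Under the amendment outcomes in Section 3 (Sample Size and Selection), the third listed change is "A change in primary focus from the 12-month to the 3-month outcomes data". Elsewhere the protocol reads as follows.

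- **Hypothesis** (Section 3, power for outcomes against directed donors): "The hypothesis is that undirected donors do no worse than directed donors 12 months after follow-up in terms of mental and physical health".
- **Power** (same subsection): 80% at a non-inferiority limit of 0.32 for 137 unspecified and 187 specified donors. The caption of Figure 2 describes the power curves as "accounting for 20% missing data at 12 months".
- **Endpoints** (Synopsis and Section 2.5): mental and physical health at 3 and 12 months. Neither list marks a primary time. Section 2.1 names the primary outcomes without a time.
- **Retention** (Section 4.2): "anyone who has failed to return their 12 months follow up assessments within 14 days will be contacted by phone", so as to obtain the primary outcome as a minimum. Section 4.3, item I, adds two further contacts for non-responders, but its subject is people presenting for donation.
- **Timetable**: recruitment to 31 January 2020 (Sections 2.2 and 3) and study end in April 2021 (Synopsis). Follow-up is timed from donation or withdrawal (Section 2.3). The study ends when recruits complete the 12-month questionnaire (Section 4.4). The December 2017 amendment text in Section 3 still refers to "the time available for analysis prior to the end of the study in April 2020".

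**The concern.** A non-inferiority conclusion needs one named time point. The mixed model in Section 2.5 has a group-by-time interaction and so yields a separate group difference at each assessment. If 3 and 12 months disagree, the protocol does not settle which one decides hypothesis (ii): Section 3 points to both, and the endpoint lists to neither.

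Retention matters because of what the protocol says about its own retrospective study (Section 1): donors with problems such as depression are those one would expect not to reply. If such loss is heavier among unspecified than specified donors, the comparison tilts towards no worse. The chase in Section 4.2 is the safeguard against this, and it is attached to the time point that is no longer the primary focus.

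The timetable raises a smaller question: whether everyone recruited can reach the 12-month questionnaire before the study closes, and whether the 20% allowance covers those who cannot.

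**Working it through.** **1. Which time does each part of the protocol use?**

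| Element | Place | Time |
|---|---|---|
| Primary focus | Section 3, amendment outcomes | 3 months |
| Non-inferiority hypothesis | Section 3, power for outcomes | 12 months |
| Missing-data basis of power | Section 3, same subsection | 12 months |
| Endpoints | Synopsis; Section 2.5 | 3 and 12, none primary |
| Chase for primary outcome | Section 4.2 | 12 months |

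The statement of change sits in the operative sample-size section of v4.1. It is not a record of superseded wording, so the mismatch lies within current text.

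**2. Reproducing the stated power.** Inputs are 137 and 187 donors, a limit of 0.32 and 20% missing. The test level comes from the initial plan in Section 3, which requires that the "lower limit of a one-sided 95% confidence interval will be above the non-inferiority limit of a standardised mean difference of 0.3", i.e. one-sided 5%. I take SD 1 and a true difference of 0.

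- Effective sizes: 137 × 0.8 = 109.6 and 187 × 0.8 = 149.6.
- SE = √(1/109.6 + 1/149.6) = 0.1257.
- Power = Φ(0.32/0.1257 − 1.645) = Φ(0.90) = 81.6%, against the stated 80%.
- Limit at 80% power = (1.645 + 0.842) × 0.1257 = 0.313.

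One-sided 2.5% gives 72.1%, which does not match. The original target (224 and 200, less 20%) gives a limit of 0.270 at 80% power, matching the stated .27. The stated power is therefore the one-sided 5% calculation with the 12-month allowance. Using 189 controls, as elsewhere in Section 3, gives 81.8%. The same subsection later attaches .38 to the revised target; I use .32, which reproduces.

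**3. Restating at 3 months.** The protocol gives no 3-month missing rate, so I assume 0% to 20%, with 137 and 187 donors.

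| Missing at 3 months | SE | Power at 0.32 | Limit at 80% power |
|---|---|---|---|
| 0% | 0.1125 | 88.5% | 0.280 |
| 10% | 0.1185 | 85.4% | 0.295 |
| 20% | 0.1257 | 81.6% | 0.313 |

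**4. Calendar.** From 31 January 2020 to the end of April 2021 is about 15 months. Taking off 12 leaves about 3 months for work-up in the last recruits. Equivalently, donation or withdrawal must occur by the end of April 2020. If work-up takes 6, 9 or 12 months (assumed), the latest enrolment month that still allows Q4 is October, July or April 2019. For the 3-month questionnaire, even a 12-month work-up allows enrolment up to January 2020.

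**5. Effect on 12-month power.** Assume uniform recruitment over the 41 months from September 2016 to January 2020 and a common work-up of w months. The fraction losing Q4 is (w − 3)/41, and the fraction observed is 0.8 × (1 − lost). The one-group columns truncate unspecified donors only, because Section 3 raises prolonged work-up only for them.

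| w | Lost | Total missing in a truncated group | Power at 0.32, both groups | Power at 0.32, one group | 80% limit, both / one |
|---|---|---|---|---|---|
| 6 | 7% | 26% | 79% | 80% | 0.32 / 0.32 |
| 9 | 15% | 32% | 76% | 78% | 0.34 / 0.33 |
| 12 | 22% | 38% | 73% | 76% | 0.35 / 0.34 |

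**The case against.** The best defence is that the protocol does state its choice, in Section 3, and refers to a predetermined analysis plan that is not shown. Nothing in the power arithmetic is specific to 12 months except the label on the 20%, so moving the label costs nothing. Section 4.3 also has a general two-contact rule that includes telephone calls. Section 2.5 adjusts for the baseline value and plans sensitivity analyses of the missing-at-random assumption.

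Much of this stands and limits the point. A reader might infer four stronger things that the document does not support.

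- **That power is lost at the primary time.** Step 3 shows it is not, if missingness is at most 20%.
- **That 3-month non-responders get no telephone contact.** Section 4.3 may be meant to reach them. It speaks of people presenting for donation and names no follow-up questionnaire, so coverage of Q3 is unclear rather than absent.
- **That the timetable cannot deliver 12-month data for late recruits.** Against April 2021, only those who donate or withdraw after April 2020 are cut off. Early withdrawers and people already in work-up, who are eligible under the inclusion criteria, can still reach Q4. The April 2020 end date would be fatal, but it is leftover text from a plan with recruitment to December 2018.
- **That non-response must favour non-inferiority, or that the time point will be picked from the results.** The former needs differential loss between the groups. The latter cannot be judged without the analysis plan.

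What the defence does not remove is the contradiction itself. An analysis plan cannot tell the study team which questionnaire to chase, and the protocol's hypothesis and its declared focus name different times.

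**Conclusion.** The point holds as an internal contradiction about the primary time point. Section 3 declares 3 months. The hypothesis, the missing-data basis of the power and the telephone chase remain at 12 months, and no endpoint list decides between them. The consequence is an unsettled primary comparison and no clearly stated chase of the 3-month questionnaire. At 3 months the stated sample gives about 82% power at 0.32 with 20% missing, one-sided 5%, and more if fewer are missing.

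The timetable is a secondary matter. Participants who donate or withdraw after April 2020 cannot give 12-month data by an end-April 2021 close. This conflicts with the end-of-study definition in Section 4.4 and is not in the 20%. The resulting 12-month power, roughly 73% to 80% at 0.32, rests on assumed work-ups of 6 to 12 months, uniform recruitment, and whether one or both groups are truncated. Even the least favourable 80% limit, 0.35, lies inside the .3 to .4 range that Section 3 gives for the minimum important difference.

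**What to change.** - Name 3 months as the primary time point in the endpoints (Synopsis and Section 2.5), in hypothesis (ii) and in the power statement of Section 3, with 12 months secondary.
- Restate the power at 3 months with an explicit 3-month missing-data rate.
- In Section 4.2, apply the 14-day telephone chase at 3 months as well as at 12, and say in Section 4.3 whether the two-contact rule covers follow-up questionnaires.
- For the 12-month analysis, state that those donating or withdrawing after April 2020 are administratively truncated, and give 12-month power with that loss added to the 20%.
- Reconcile Section 4.4 with the April 2021 close, and update the leftover April 2020 date in Section 3.

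The cost is protocol wording plus reminder calls by the existing team at one more assessment. As an illustration, if one in five of the 758 targeted participants had not replied at 14 days (assumed), that would be 0.2 × 758, or about 152 people to telephone over the whole study.

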Transplant co-ordinators at each of the 23 UK transplant centres will ask potential donors approaching their units if they would be interested in participating in the study. This does not equate to being consented into the study, but simply facilitates further information gathering regarding our work. This will occur either at the initial telephone contact between the potential donor and the transplant centre or at the first clinic consultation with the transplant co-ordinator, depending on local practice protocols. Potential donors already being worked-up will also be given the opportunity to contact the study team for recruitment into the study.

Once a potential donor agrees to find out more about the study, the local transplant co-ordinator will facilitate contact with the research team by either giving the team's contact details to the potential donor, or (with the donor's permission) pass on their preferred contact details to the research team. The study's manager will be notified of individuals interested in the study. The research team will contact potential participants by phone, email or post to provide further information, discuss the study and provide participant information sheets. Those that indicate a willingness to participate will be enrolled in the study subsequent to completion of the relevant consent forms. The emphasis of the study is to cause minimal inconvenience to local transplant units and human resources. As such, once a transplant co-ordinator has facilitated the contact between the potential donor and the study team, no further involvement will be needed and all subsequent administrative and research work will be co-ordinated by the study's manager or investigators.

The control group will consist of individuals who are donating to friend or relative (specified donors). Control (specified) donors will be recruited in a similar consecutive manner by

transplant co-ordinators. Control donors that do not proceed to specified donation will still be asked to participate in the study in order to provide robust data for comparison.

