2.4 Study Outline

2.5 Trial Statistics and Data Analysis

The study endpoints will be:

- i) time from enquiry to donation (for those that proceed to donation)
- ii) mental and physical health at 3 and 12 months post donation, compared to directed donor controls

All primary analyses will be undertaken by the study statistician and investigator / research fellow in accordance with a predetermined analysis plan.

Descriptive analysis will be used to describe the proportion of people who withdraw or proceed to donation, and the reasons for failing to proceed. The analysis will include all individuals enquiring about donation, with the dependent variable an indicator for each proceeding to donation. Centre-level structural and attitudinal factors identified in our

parallel study (IRAS 170483) will be included in the models to determine whether these variables explain variation in donation rates.

Descriptive analysis will be used to compare baseline variables for individuals that express an interest in donation that: i) the transplant team withdraw from donation; ii) those who decide not to proceed; iii) those that proceed to donation; and iv) the specified kidney donor control group, who either proceed or do not proceed to donate. Linear or logistic mixed-effects models will be used to estimate difference in outcome variables at the 3 and 12 months follow-up assessments between the groups at the outcome assessments. Group membership and follow-up assessment (time) will be included in the models as dummy variables. Interaction terms for group and time will allow for assessments of differences at individual time points. Models will adjust for potential demographic confounders measured at baseline (e.g. age, sex, education, ethnicity) and the baseline level of the outcome variable. Missing outcome data is under the assumption that data is missing at random. Sensitivity analysis will be performed to assess this assumption.

The analysis of qualitative data will be performed using the Framework (thematic) approach as described above.

3. Sample Size and Selection

Focus Groups

The two focus groups will recruit 8-12 potential or actual unspecified kidney donors each. These will be volunteers identified by UK transplant co-ordinators.

Questionnaires

Consecutive people contacting each of the transplant centres in the UK between September 2016 and October 2019 will be recruited to participate in the study.

Initial Recruitment Plan

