Any individual contacting a transplant centre to enquire about unspecified donation, who proceeds beyond the initial telephone conversation, and is able to give informed consent will be considered as a potential study participant. Non-English speakers will be included and adequate translation facilities will be provided. Individuals who have already begun the donation work-up process at the time of study commencement will also be eligible for recruitment provided they are more than 2 weeks away from donation. Control participants will be recruited from those individuals contacting a centre in order to donate to a known individual.

Exclusion criteria

Any individual who declines to participate at any stage will be excluded from the study. Individuals lacking capacity will also be excluded as will any individual not eligible to donate in UK. This includes foreign nationals who are unable to donate altruistically in their country of residence or prisoners.

4. Study procedures

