Appendix 4:

		Phase 1: Potential donors				Phase 2: Outcomes			
		Recruitment		Pre donation		Donation		Follow-Up	
Data (source)		Pre-enrolment	Enrolment	Baseline	Pre-op (1 week)	Surgery	Post-op	Follow-up 3 months	Follow-up 12 months
Enrolment	Initial contact (Centre)	X							
	Referral (Centre)	X							
	Eligibility screen (Trial manager)		X						
	Informed Consent (Trial manager)		X						
Assessments	Baseline demographic data			A					
	Personality: TIPI (Questionnaire)			A					
	Social support: MSPSS (Questionnaire)			A	A			A	A
	Peri-operative physical outcome data (NHSBT)				A		D		D
	Surgical procedure data (NHSBT)					D			
	Withdrawal (Questionnaire & Centre data)			W	W				
	Rosenberg (Questionnaire)			A	A			A	A
	SWLS (Questionnaire)			A	A			A	A
	PHQ9 & GAD7 (Questionnaire)			A	A			A	A
	Flourishing Scale			A	A			A	A
	Decision Regret Scale							A	A
	SF12 (Questionnaire)			A	A			A	A
	Client Service Receipt Inventory (Questionnaire)			A	A			A	A
	In-House Questionnaire			A	A			A	A

X= recruitment and centre level data (pre-consent)

A= Data from all potential donors

D= Data for donors only

W= Data for withdrawn only

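### Participants enter at different stages of the pathway while the donation rate is said to cover everyone who enquires, so the donation share is biased upward and centre rates can differ through recruitment practice

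*Protocol*

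**What the plan says.** **Entry point.** Section 2.2 (Interview and Questionnaire Recruitment) has co-ordinators raise the study "either at the initial telephone contact between the potential donor and the transplant centre or at the first clinic consultation with the transplant co-ordinator". Which of the two applies is left to each centre's usual way of working. It adds: "Potential donors already being worked-up will also be given the opportunity to contact the study team for recruitment into the study". Section 3 (Inclusion criteria) admits a person enquiring about unspecified donation "who proceeds beyond the initial telephone conversation". It then says "Individuals who have already begun the donation work-up process at the time of study commencement will also be eligible for recruitment". The condition attached is that surgery must be over a fortnight off. The Study Synopsis also admits people already in work-up. Neither the Synopsis nor Section 2.2 limits this to study commencement.

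**Analysis.** Section 2.5 starts the time endpoint at enquiry. For the donation analysis, where each person is coded as proceeding or not, it says "The analysis will include all individuals enquiring about donation". Centre-level factors enter those models. Section 3 (Precision and power with respect to donation rates) uses case-mix adjusted centre rates to pick out centres well below or above the average. It names Cox regression for time to donation.

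**Dates.** Section 3 (Amendment outcomes) asks donors, at Q2, to estimate when they first contacted the service. Appendix 4 separately lists initial contact and referral as centre data obtained before consent.

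**Baseline.** Section 2.3 intends Q1 to describe participants before work-up begins.

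**The concern.** A person who drops out before the point at which their centre introduces the study cannot be enrolled. The enrolled sample is therefore those who have survived in the pathway to entry, which is a different population from enquirers. Losses before entry are all non-donors, so the share who donate is too high as an estimate for enquirers.

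Entry stage may also depend on the centre, which is the unit being compared. A centre that raises the study at clinic misses withdrawals between call and clinic, and a centre that raises it at the call can capture them. The first centre would then show the higher donation rate with no difference in how it treats potential donors.

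Objective (i) is to identify and explain regional variation, and centre rates are to be read as performance. An artefact of recruitment could be attributed to staff attitudes, expertise or resources.

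**Working it through.** **1. The plan's own figure and its denominator.** The 95% half-width for a proportion is 1.96 × √(p(1−p)/n). With p = 0.35 and n = 380 this is 1.96 × √(0.35 × 0.65/380) = 0.048, matching the stated figure of about ±5%. The expected donors are 0.36 × 380 = 136.8, the stated 137. Both results show that the rate is to be estimated on recruited participants. They also show that a conversion rate defined from first contact (36%, Section 3, Initial Recruitment Plan) is carried over to recruited participants unchanged.

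**2. Share observed when entry is late.** Let f be the fraction of eventual non-donors who leave before the entry point. It is assumed here, because the protocol gives no value. If no eventual donor is lost:

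observed share = 0.36 / (0.36 + 0.64 × (1 − f))

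| f | Calculation | All entrants late | Shift, all late | Shift, half late |
|---|---|---|---|---|
| 10% | 0.36/0.936 | 38.5% | +2.5 points | about +1 |
| 25% | 0.36/0.840 | 42.9% | +6.9 points | about +3 |
| 50% | 0.36/0.680 | 52.9% | +16.9 points | about +8 |

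The last column averages the late share with 36%. For example, at f = 25% it is 0.5 × 0.36 + 0.5 × 0.429 = 0.394.

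**3. Comparison with the planned precision.** Section 3 gives about ±9 points per centre under empirical Bayes at the revised target. That figure cannot be checked, because the simulation inputs are not given. A 9-point shift needs 0.36/(0.36 + 0.64(1 − f)) = 0.45, so f = 1 − (0.36/0.45 − 0.36)/0.64 = 0.31, with all entrants late.

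**4. Time to donation.** Two centres with an identical process were simulated, one enrolling at enquiry and one later. The assumptions were 36% donors, donation times averaging 10 months, mean time to withdrawal of 2, 4 or 8 months, and late entry uniform over 0–3 or 0–6 months.

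- Donation share: 36% against 40–62%.
- Median enquiry-to-donation time in donors: about 9.4 against 9.6–10.2 months.
- Hazard ratio for the late centre, clock from enquiry, withdrawals censored, entry time ignored: 0.88–0.99.
- The same with delayed entry: 0.95–1.01, within sampling error of 1.
- If withdrawn people stay in the risk set and entry time is ignored: 1.10–2.08.

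The rate bias appears in every scenario. The hazard-ratio bias is modest with withdrawals censored, and its direction depends on how withdrawals are handled.

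**The case against.** Several objections have force.

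- **Delayed entry.** A reader might infer that the Cox analysis ignores delayed entry. The protocol is only silent. Section 2.5 defers to an analysis plan that is not at hand, and entry times are ordinary content for such a plan.
- **Pre-consent data.** A reader might infer that early withdrawals are never counted. Appendix 4 lists centre contact and referral data before consent, which could supply the enquiry denominator. The protocol does not link them to the rate analysis, however, and the precision figures use recruited participants.
- **Mid-work-up entry.** Section 3 ties it to study commencement, which would make it a one-off group. The Synopsis and Section 2.2 carry no such limit, so its extent is unclear.
- **Call against clinic.** Section 2.2 describes when interest is raised; consent follows later through the central team. People who stop at the first call are excluded everywhere. Only losses after that call can create a call/clinic gap, and the two larger values of f in the table have no source in the document.
- **Slower times.** A reader might infer a large spurious slowing. Hazard ratios near 0.80 and 0.67, for entry 3 and 6 months late, arise if hazards are constant and everyone in the centre enters late. In that model the donation share stays at 36%, so those ratios cannot be combined with the 43–53% shares above.
- **Weight.** Section 3 disclaims ranking and plans shrunken, case-mix adjusted rates. The Synopsis makes quality of life and mental health primary, with barriers secondary.

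These points limit the size and certainty of the concern. They leave the mismatch between the stated denominator and the people enrolled. Shrinkage and case-mix adjustment do not remove the effect of entry stage unless stage is in the model.

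**Conclusion.** The concern holds as a defect in the protocol's own text, because the eligibility and recruitment rules cannot deliver the population that Section 2.5 describes. Followed as written, the overall donation share is biased upward as an estimate for enquirers. Centre rates can differ through recruitment practice alone if entry mix varies by centre. If the mix were the same everywhere, the overall bias would remain without spurious centre gaps.

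With a true rate of 36% and all entrants late, the share would be 38.5%, 43% or 53% for early losses of 10%, 25% or 50% of eventual non-donors, and the shift would be about half that if half enter late. The documents give neither the early-loss fraction nor the share of late entrants, so the actual size is unknown. The effect on hazard ratios is uncertain and may be small.

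Two related points also stand. A first-contact date asked only of donors gives no enquiry time for non-donors. Q1 cannot precede work-up for someone who enters during it.

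**What to change.** - In Section 2.5, replace the reference to everyone enquiring with the population actually sampled.
- Record stage at entry (call, clinic, in work-up), consent date and centre-recorded enquiry date for donors and non-donors. Use the initial-contact data in Appendix 4, and do not rely only on the date donors recall at Q2.
- Base centre donation rates on participants enrolled before work-up, with entry stage (call or clinic) as a covariate, or report mid-work-up entrants separately.
- Report conversion from enquiry using the pre-consent centre counts.
- State that the Cox model takes participants as at risk from consent, with the clock from enquiry, if the SAP does not already say so. This addresses the time analysis but does not repair the raw proportion, which needs the steps above.
- Reconcile the Synopsis, Section 2.2 and Section 3 on who may enter during work-up, and reconcile the Section 2.3 description of Q1 with that rule.

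The cost is wording, a few extra variables, and slightly fewer observations or somewhat wider intervals.
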